12.2.2. CARDIOPULMONARY BYPASS TIME

Cardiopulmonary bypass time will be summarized by central tendency and variability estimators such as mean, median, standard deviation and interquartile range.

12.2.3. DEVICE TECHNICAL SUCCESS AND PROCEDURAL SUCCESS

The number and percentage of enrolled patients experiencing device technical success and procedural success will be calculated.

12.2.4. HEMODYNAMIC PERFORMANCE

The following parameters will be summarized (mean, median, standard deviation and interquartile range) at baseline, Discharge and 6 month Follow up visits for all subjects in the study valve population: mean gradient, peak gradient, effective orifice area (EOA), EOA index, performance index, cardiac output, cardiac index, valvular regurgitation (including paravalvular leak), end systolic and end diastolic left ventricular volumes. Valvular regurgitation will be summarized by the number and percentage of subjects in each level of regurgitation. An analysis stratifying by valve size will also be performed.

12.2.5. LENGTH OF HOSPITAL STAY AND TIME IN INTENSIVE CARE UNIT

The length of hospital stay and length of time in intensive care unit will be summarized (mean, median, standard deviation and interquartile range) for the enrolled cohort.

12.3. SAFETY DATA

- All cause mortality
 - Study valve-related mortality
- Thromboembolism (Stroke, TIA, and Non cerebral embolism)
- Valve Thrombosis
- Major Bleeding event

- Endocarditis (study valve)
- Structural valve deterioration
- Non Structural valve deterioration
 - Paravalvular Leak minor
 - Paravalvular Leak major
 - Other non SVD
- Hemolysis
- Reoperation
 - Trial valve reoperation
- Study valve explants
- Implant-related new or worsened cardiac conduction disturbance requiring permanent pacemaker implant
- Renal Failure
- Respiratory Failure
- Deep Sternal Wound infection

Early adverse events within 30 days of procedure will be reported as the number of events divided by the number of enrolled subjects. Linearized rates will be used to summarize adverse events for the late (>30 days) post-operative period. The linearized rates will be calculated as the number of late events divided by the total number of late-subject years.

Percentages for the early events and linearized rates for the late events also will be calculated for all other complications observed in the trial.

Actuarial rates based on the method of Kaplan - Meier will be calculated for each of the safety endpoints at thirty days and six months; the number of subjects at risk for death will be reported at each of these intervals.

On top of Implant-related new or worsened cardiac conduction disturbance requiring permanent pacemaker, the counts and percentage of subjects who experience new or worsening cardiac rhythm or conduction disturbances will be calculated at each follow-up visit. The identification of “new and worsening” cardiac rhythm or conduction disturbance will be based on a comparison to the previous visit.

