8.2. Eligibility Inclusion Criteria

Subjects will be required to meet all inclusion criteria:

1. **Subject is 18 years or older**
2. **Subject is symptomatic for aortic stenosis (AS) or mixed aortic stenosis and aortic insufficiency (AS/AI) disease for which isolated surgical aortic valve replacement without concomitant procedures is indicated according to International guidelines.**
3. **Surgery starts with and is intended to be completed via a minimal invasive surgical approach. MIS is defined as one of the following approaches: upper hemi-sternotomy and right anterior thoracotomy.**
4. **Surgery is intended to be completed with an EDWARDS INTUITY Elite**
5. **Subject has signed and dated the investigation informed consent forms prior to registry-specific procedures are performed.**
6. **Subject is geographically stable and agrees to attend follow-up assessments as specified in the protocol and informed consent.**

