In the operating room, the intra-operative exclusion criteria will be assessed by careful examination of the valve anatomy, valve condition and associated structures. Any other intra-operative exclusion criteria or eligibility exclusion criteria may be assessed throughout the procedure.

Adverse events for enrolled patients are collected from the time the subject is in the operating room.

Enrolled patients, due to an intra-op Exclusion criteria can be excluded (defined as intra-op screen failure). The reason for ineligibility will be explained to them and will be documented into the eCRF. Subjects will then be followed by their primary health care provider per best medical practice.

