12.1.1. ENROLLED COHORT

A subject will be considered enrolled into the registry when he/she has signed the informed consent, met all the registry eligibility criteria.

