12.1.2. PER PROTOCOL COHORT

The per protocol cohort will consist of all enrolled patients that leave the operating room with the registry valve in place and had an AVR MIS surgery procedure. All summaries of the safety endpoints and other safety data will be based on the per protocol cohort. The summaries of the primary, secondary and patient related endpoints will also be based on the per protocol cohort.

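### The early safety rate divides events by enrolled subjects, while the cohort rule puts all safety summaries on the per protocol cohort; name one cohort and count subjects, not events

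*Combined protocol and SAP*

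**What the plan says.** Section 12.3 gives the rule for the listed safety endpoints: "Early adverse events within 30 days of procedure will be reported as the number of events divided by the number of enrolled subjects". It then adds: "Percentages for the early events and linearized rates for the late events also will be calculated for all other complications observed in the trial". The word percentages is attached explicitly to those other complications and reaches the listed endpoints through the word also. Section 12.3 further plans Kaplan-Meier rates at thirty days and six months for each safety endpoint, with the number at risk reported for death.

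Section 12.1.2 sets a different cohort: "All summaries of the safety endpoints and other safety data will be based on the per protocol cohort". That cohort is "all enrolled patients that leave the operating room with the registry valve in place and had an AVR MIS surgery procedure". Appendix C adds that no intra-operative exclusion criterion may be met.

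Enrolment does not require an implant. Section 12.1.1 says: "A subject will be considered enrolled into the registry when he/she has signed the informed consent, met all the registry eligibility criteria". Section 9.4 confirms that subjects can drop out in the operating room after enrolment: "Enrolled patients, due to an intra-op Exclusion criteria can be excluded (defined as intra-op screen failure"). It passes them to their own health care provider. Section 9.6.1 treats two other groups differently. Subjects with an attempted but unsuccessful implant, and those converted to full sternotomy once the implant procedure has begun, are followed for 30 days with adverse events collected.

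**The concern.** Two things are unclear about a rate that will be quoted as the registry's early complication rate. The first is whose events are counted and over whom. Sections 12.1.2 and 12.3 give different answers, and an analyst trying to obey both could take events from the narrower cohort and divide by the wider one. The second is the unit. A count of events over a count of subjects is not a proportion of patients once anyone has the same event twice, and section 12.3 has no first-event rule.

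Short-term safety is the first secondary objective (section 6), and section 2.2 says the data will support publications and marketing information. Two analysts following this text in good faith could publish different 30-day rates from the same database. Events in failed-implant and converted subjects, who are of obvious safety interest, could also disappear from the summaries although they were collected.

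**Working it through.** The plan states no safety rate, expected event count or safety precision, so there is no figure on this point to reproduce. Its one computable figure, power above 90% for cross-clamp time, does reproduce: 15 / (16 × √(1/479 + 1/300)) = 12.7, giving power of about 1.00. It has no bearing here.

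**Step 1. Who is in which cohort.**

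| Group | Enrolled (12.1.1) | Per protocol (12.1.2, Appendix C) | 30-day follow-up |
|---|---|---|---|
| Valve in place, minimally invasive procedure | yes | yes | yes (9.8.2) |
| Implant attempted, not achieved | yes | no | yes (9.6.1) |
| Converted after implant procedure began | yes | no | yes (9.6.1) |
| Intra-operative screen failure | yes | no | none specified; passed to own provider (9.4) |

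On the last row, sections 5 and 9.8.1 say in general terms that all enrolled subjects are assessed at 30 days, but the specific text in 9.4 points the other way. Adverse events are collected from entry to the operating room (9.4), so intra-operative events in this group may be captured while later ones may not.

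**Step 2. What the rule returns.** Let E be enrolled subjects, C the subjects whose events are counted, A those in C with at least one event, and V the events. The plan's figure is V/E; the share affected is A/C. With f = 1 − C/E and r = V/A − 1,

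V/E = (A/C) × (1 − f) × (1 + r).

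**Step 3. Numbers.** E = 300 is the planned maximum (section 12.5). The values of f, r and A are assumptions, because the documents give none of them.

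- Cohort mismatch only (r = 0), share affected 5%: f = 5%, 10%, 20% gives 4.75%, 4.5%, 4.0%.
- Repeats only (f = 0), 15 affected of 300 (5.0%): r = 10%, 20%, 30% gives 5.5%, 6.0%, 6.5%.
- Both, with 15 events in 12 subjects (r = 25%): the plan reports 15/300 = 5.0%. The share affected is 12/300 = 4.0% at f = 0, 12/285 = 4.2% at f = 5%, and 12/270 = 4.4% at f = 10%.
- The two effects cancel when r = 1/(1 − f) − 1: f = 5%, 10%, 20% needs r = 5.3%, 11.1%, 25%.

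For endpoints that can recur, the net direction is therefore not known in advance. For those that cannot, or hardly can, within 30 days, only the cohort term is left, and it acts downward.

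**Step 4. Subjects who cannot have the event.** This question remains under either cohort. If 3–10% of subjects already had a pacemaker, a rate of 8.0% among the rest would appear as 0.08 × 0.97 = 7.8% to 0.08 × 0.90 = 7.2%. Three deep sternal wound infections are 3/300 = 1.0% overall, but 3/240 = 1.25%, 3/210 = 1.43% or 3/150 = 2.0% of sternotomy subjects if 20%, 30% or 50% had thoracotomy access. These inputs are also assumed.

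**The case against.** Section 12.1.2 is categorical, and one can argue that it governs. Section 12.3 would then be loose wording for the same per protocol subjects, numerator and denominator would agree, and nothing would be diluted. That is a possible reading, and it is why one cannot assert that subjects without a valve do dilute the rate. But enrolled is a defined term with its own section, and nothing says which rule prevails. The contradiction stands.

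On repeats, the 30-day Kaplan-Meier rates would normally be first-event, subject-level estimates. Table 2 counts a cluster of transient neurological events once, and death cannot recur. This is largely right. What remains is the separate events-over-subjects figure for endpoints such as major bleeding, embolism and reoperation. Kaplan-Meier also has to be run on some cohort, so it inherits the unresolved choice.

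A reader might go further and infer that the pacemaker and deep sternal infection rates are wrong because subjects with an existing pacemaker, or with thoracotomy access (allowed under section 8.2: "MIS is defined as one of the following approaches: upper hemi-sternotomy and right anterior thoracotomy"), stay in the denominator. The documents do not support that. The safety objective is descriptive, and a rate over everyone treated is a legitimate summary. The listed exclusions do not name an existing pacemaker, but section 8.3 also excludes device contra-indications, and the Instructions for Use are not available here. The baseline-rhythm wording in procedural success (section 9.6) is no precedent: it limits which pacemaker implants count as failures, while section 12.2.3 still reports success over enrolled patients.

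Finally, the shifts may be small against sampling error. At 4% with n = 300 the standard error is √(0.04 × 0.96/300) = 1.1 percentage points. That limits the consequence; it does not make an ambiguous definition acceptable.

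**Conclusion.** The early safety rate is not well defined as written. Sections 12.1.2 and 12.3 name different cohorts. Applying both literally can put per protocol events over enrolled subjects, with a downward bias equal to the share of enrolled subjects outside per protocol. Separately, for events that can recur, the figure is not the proportion of patients affected.

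The size cannot be established from the documents. With 5–20% of enrolled subjects outside per protocol, a 5% rate would read 4.75–4.0%. With 10–30% repeat events, it would read 5.5–6.5%. These ranges rest wholly on the assumed shares. The conclusion itself rests only on the text of sections 9.4, 9.6.1, 12.1.1, 12.1.2 and 12.3 and Appendix C. Mortality is unaffected by the repeat-event part. At-risk denominators for pacemaker and sternal infection are a useful supplement, not a correction of an error.

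**What to change.** 1. Reconcile sections 12.1.2 and 12.3 by naming one cohort for both numerator and denominator of the early rates, and state that the Kaplan-Meier rates use the same one.
2. Redefine the early rate in section 12.3 as the number of subjects in that cohort with at least one event within 30 days of the procedure, divided by the number of subjects in that cohort. Give the number of events alongside.
3. If per protocol is chosen, tabulate separately the 30-day events of subjects with an attempted but unsuccessful implant and of converted subjects, so that they are not lost. If enrolled is chosen, state how intra-operative screen failures without 30-day data are handled. In either case, report how many there are.
4. Optionally, within the chosen cohort, also show the pacemaker rate among subjects with no pacemaker at baseline and the deep sternal wound infection rate by access route.

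The cost is mainly a change of wording. Follow-up of failed-implant and converted subjects is already collected (section 9.6.1), as are medical history and ECG (section 9.5) and surgical approach and conversion (section 9.6.1). The sample size does not change. The one possible extra burden is 30-day status for intra-operative screen failures, and it arises only if the enrolled cohort is chosen and their follow-up is to be complete.

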9.8. Follow-up Visits Registry Procedures

9.8.1. FOLLOW-UP VISIT WINDOWS

Post-procedure clinical evaluation will be performed on all enrolled subjects at 30-days and 6-months post-implant date. Follow-up at 30 days- will be conducted by phone. All follow-up data will be documented on the CRF.

Patient assessments will be done according to the sites standard of care.

It is important that the follow-up visit schedule is maintained as closely as possible for all subjects. Edward's recognizes that subjects may not be able to return for all scheduled visits at precisely the date required, and therefore, an acceptable window of time for the 30 day follow-up period is described in Table 1. Registry visits should be scheduled as close to the earliest portion of the window for the follow-up period so that cancellations and visit rescheduling can still be conducted within the required time period.

TABLE 1. SCHEDULED FOLLOW-UP VISIT DAYS AND APPLICABLE VISIT WINDOWS

Visit	Visit Window days	Timing from Implant (Day 0)
Screening		Day -30 to Day -1
Discharge		Post-op - Day of Discharge
POD 30	+/- 7	Day 23 to Day 37
POD 180 (if applicable)	+/- 45	Day 135 to Day 225

Protocol required registry follow-up not performed will be considered a missed visit.

9.8.2. 30 DAYS FOLLOW-UP VISIT: REQUIRED PROCEDURES AND EVALUATIONS

The 30 day follow-up visit shall be performed by phone. The clinical evaluation and data requirements for the registry subjects at POD 30:

- Adverse Events: Post-operative procedure or cardiac related events that resulted in medical or surgical intervention; all other serious adverse events per investigators decision using the available adverse event code list will also be collected.
- NYHA classification

9.8.3. 180 DAYS (6 MONTHS) FOLLOW-UP VISIT: REQUIRED PROCEDURES AND EVALUATIONS

The 6 month follow-up visit shall be performed at the investigational site, if applicable. The clinical evaluation and data requirements for the registry subjects at POD 180:

- Adverse Events: Post-operative procedure or cardiac related events that resulted in medical or surgical intervention all other serious adverse events per investigators decision using the available adverse event code list will also be collected.
- Medical examination: HR, BP, NYHA classification, weight
- ECG 12 lead
- Echocardiography data will be collected (if available and CD will be sent to CoreLab)
- Anticoagulation therapy
- Coagulation profile: INR and PT

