9.9.1. SUBJECT REGISTRY COMPLETION

Registry subjects complete and exit from the registry when no additional follow-up visits, procedures, or data collection are required. Once participation is completed subjects will then continue to be followed by their primary health care provider per standard medical practice.

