18.1. APPENDIX A: Table of procedures and flowchart

Time Periods and Assessments	Preoperative	Operative	Discharge	30 Days (Phone)	6 Months (180 days)
Informed Consent	X				
Medical History Aortic Valve Etiology and diagnosis	X				
Inclusion Criteria / General Exclusion Criteria	X				
Medical Examination	X		X		X
Height	X				
Weight	X		X		X
Heart rate and Blood Pressure	X		X		X
NYHA	X		X	X	X
Demographics (DOB& gender)	X				
LVEF	X				
Logistic Euroscore I and II	X				
Pregnancy test (If applicable) ¹	X				
Health care utilization (Length of stay ICU and war0064)			X		

Time Periods and Assessments	Preoperative	Operative	Discharge	30 Days (Phone)	6 Months (180 days)
Implant Procedural Data and timing		X			
Intra-operative Exclusion criteria evaluation		X			
12 Lead Electrocardiogram (EKG)²	X		X		X
Transthoracic Echocardiography and Doppler	X ³		X ⁴		X ⁴
Current Anticoagulation Therapy	X		X		X
Coagulation profile: INR and PT⁵	X		X		X
Blood Studies RBC, WBC, HGB, HCT, Reticulocytes, Platelet counts, Serum Creatinine	X		X		X
Fitness for hospital discharge			X		
Quality of Life (QoL): EQ-5D SF-36	X				X
Adverse Events		X	X	X	X

1 - Pregnancy test is required for female subjects who are not post-menopausal or surgically sterile (urine)

2 - For EKG machine generated reports the Investigator must verify that the cardiac rhythm is correct and sign and date the final EKG report

3 - If available Pre-op echocardiography within 3 months of planned implant date and including echocardiographic data in the format required per the echocardiography guidelines

4 - If available echocardiography data will be collected

5 - Required only if patient is being treated with a coumadin derivation medication

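### Six-month Kaplan-Meier and linearized rates for findings seen only on a scheduled echo depend on visit timing as well as on how many patients have the finding

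*Combined protocol and SAP*

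**What the plan says.** Section 12.3 plans that actuarial rates by the method of "Kaplan - Meier will be calculated for each of the safety endpoints at thirty days and six months". For events after 30 days it adds: "The linearized rates will be calculated as the number of late events divided by the total number of late-subject years". Its endpoint list includes "Paravalvular Leak minor", major leak, structural deterioration and other non-structural deterioration, and no echo-detected finding is excepted.

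In Table 2 (Section 11.2), a leak of grade 3+ or more counts as major whether or not there are symptoms or an intervention. Structural deterioration may be established by clinical investigation, which should include periodic echo.

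Post-operative echo is scheduled at discharge and at six months only. Appendix A, footnote 4, reads: "If available echocardiography data will be collected". Between the two, Section 9.8.2 says: "The 30 day follow-up visit shall be performed by phone". Table 1 sets the POD 180 window at "Day 135 to Day 225", and Section 9.8.1 asks for early booking: "Registry visits should be scheduled as close to the earliest portion of the window for the follow-up period". On the end of follow-up, Section 9.9.1 says: "Registry subjects complete and exit from the registry when no additional follow-up visits, procedures, or data collection are required".

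Neither Section 12.3, Section 12.4 nor Table 2 says how to date a finding first seen on echo, when to censor a subject without one, or how the six-month read-out relates to the 90-day window.

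**The concern.** Kaplan-Meier needs an event date and censoring that is unrelated to detection. For an echo-only finding at six months, one visit may supply both: it dates the finding in those who have it and, if they then leave the registry, ends follow-up in those who do not. The curve then describes when subjects were imaged as well as how many had a leak. A leak first imaged after Day 180, though in window, adds nothing to a Day 180 estimate.

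The linearized rate has a related weakness. A leak missed at discharge because no echo was available, then seen at six months, is counted as a late event over late exposure although its onset is unknown.

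At stake are the six-month leak and valve-deterioration rates. Complication rates at 30 days and six months are stated safety endpoints (Section 1), and Section 2.2 says the data will support publications and marketing information.

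**Working it through.** The plan gives no figure for these rates, so there is none to reproduce. (Its one computed design figure, the power for cross-clamp time, does not bear on this point.)

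**Inputs from the documents:** 300 subjects (Section 12.5); window Days 135-225 (Table 1); late period from Day 30 (Section 12.3).

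**Assumptions:** a share p of subjects has a finding first seen at the six-month echo, independent of visit day; everyone is imaged once in window; the finding is dated on the echo day; six months is read at Day 180. The main case is p = 5%, or 15 of 300, with 2% and 10% as the range. Two censoring rules are tried for subjects without the finding: at the visit, and at Day 225.

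**Kaplan-Meier, censored at the visit.** With visits even over m days, when k visit days remain a share 1/k of the risk set is seen, and a share p of those has the finding. So the estimate is 1 − Π(1 − p/k) over visit days up to Day 180.
- Days 135-225: 91 days, 46 of them by Day 180, so k runs from 91 to 46. Σ1/k = 0.699, and the estimate is 3.4%.
- Days 135-165: 31 days, k from 31 to 1. The product gives 18.4%.
- Days 181-225: no event by Day 180, so 0%.
- All visits on Day 135, or all on Day 180: 15/300 = 5.0%.

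**Kaplan-Meier, censored at Day 225.** The estimate is p times the share of visits by Day 180. Even spread: 0.05 × 46/91 = 2.5%. Days 135-165: 5.0%. Days 181-225: 0%.

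Simulation of 300-subject registries agrees:

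| Visits (p = 5%) | KM at Day 180, censored at visit | KM at Day 180, censored at Day 225 | Proportion of imaged subjects |
|---|---|---|---|
| Days 135-225 | 3.4% | 2.5% | 5% |
| Days 135-165 | 18.4-18.5% | 5.0% | 5% |
| Days 181-225 | 0% | 0% | 5% |
| All Day 135 or all Day 180 | 5.0% | 5.0% | 5% |

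For the even spread with censoring at the visit, prevalences of 2%, 5% and 10% give 1.4%, 3.4% and about 6.7%.

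**Where the 18% comes from.** About 300/31 ≈ 10 subjects remain on Day 165 and none after it. Each late-seen leak therefore makes a large step, and the Day 180 value is carried forward from an emptied risk set.

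**Linearized late rate**, exposure ending at the visit: 15 ÷ [300 × (mean visit day − 30)/365.25].
- All on Day 135: 15/86.2 = 17.4 per 100 subject-years.
- Even over Days 135-225 (mean 180): 15/123.2 = 12.2.
- Even over Days 181-225 (mean 203): 15/142.1 = 10.6.

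If exposure of the 285 finding-free subjects ran to Day 225 instead, the Day 135 case would be 15 ÷ [(285 × 195 + 15 × 105)/365.25] = 15/156.5 = 9.6, and the Days 181-225 case 15 ÷ [(285 × 195 + 15 × 173)/365.25] = 15/159.3 = 9.4. Visit timing then hardly matters, but the choice of exposure rule moves the Day 135 figure from 17.4 to 9.6.

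**The case against.** Much of the opposing case stands.

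- **Prevalence still counts.** A reader might infer that the rate reflects booking rather than how many patients have a leak. It does not: within a fixed schedule the estimate rises roughly in step with prevalence.
- **A visit-based figure is already planned for leak.** Section 12.2.4 reports regurgitation, including paravalvular leak, as number and percentage per level, and Section 7.2 has it read by the core laboratory. That is unaffected by visit day. It does not cover the minor and major leak safety endpoints as Table 2 defines them, nor structural or other non-structural deterioration, and no interval is planned.
- **Upward inflation is not established.** A reader might infer that early booking will overstate leak more than threefold. That needs censoring at the visit. Section 9.9.1 points that way, but Section 9.9.2 expects patients to continue until the sponsor gives written notice, and Section 12.3 sets no rule. With censoring at Day 225 the inflation vanishes.
- **The 0% case is extreme.** It needs every visit after Day 180, against the early-booking instruction, and an exact Day 180 read-out, which the plan does not state.
- **Some of these events have real dates.** Leak or deterioration found through intervention, reoperation, death or autopsy does not share the problem of an echo-only finding.
- **A discharge echo finds a detectable leak present since surgery.** This limits the linearized argument to subjects not imaged then, or to findings that arise later. The 5% is not from the documents.
- **No test or decision uses these rates.** The safety objective is to describe. A reader might also infer misleading differences between sites, but Section 12.3 plans no site-level safety rates.

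The events committee's charter, which is not among the documents, might contain a dating rule. That would not settle the censoring rule or the read-out day.

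**Conclusion.** The point holds for echo-only findings. Section 12.3 prescribes time-to-event and person-time summaries for outcomes with no known onset date, first seen at discharge or at a single echo in a 90-day window centred on Day 180. Kaplan-Meier then depends on visit timing under both censoring rules tried: at an assumed 5%, the even spread gives 3.4% or 2.5%. Early-clustered visits over Days 135-165 give about 18% with censoring at the visit, an unstable figure, and the correct 5% with censoring at Day 225. The linearized rate runs from 17.4 to 10.6 per 100 subject-years when exposure ends at the visit, and is nearly flat when it runs to Day 225.

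The sizes rest on the assumed prevalence, the visit spread, dating at the echo and a Day 180 read-out. The mechanism does not rest on the 5%. One practical consequence is that the report could carry two six-month leak figures, from Sections 12.2.4 and 12.3, that disagree. Severity is moderate because the rates are descriptive.

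**What to change.** Amend Section 12.3 in one paragraph:

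- Keep Kaplan-Meier and linearized rates for events with a clinical, procedure or death date, including leak or deterioration that leads to re-intervention or death.
- Report echo-only findings (minor leak, grade 3+ leak without intervention, echo-detected structural or other non-structural deterioration) as the proportion of subjects with an evaluable echo at discharge and, separately, in the POD 180 window. Give numerator, denominator and an exact 95% confidence interval, in a form consistent with Section 12.2.4. At 15 of 300, for example, the exact interval is 2.8% to 8.1%.

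This needs no extra data or visits. The cost is that these endpoints lose a single time-to-event summary.
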